8.1.5 Dose delays

If patients do not meet the criteria below on the day of the scheduled treatment, the administration of the dose will be delayed.

1. No evidence of progressive disease or relapse prior to the start of each cycle; however, treatment may continue, at the judgment of the investigator, in patients with only extramedullary CNS and/or testis relapse.
2. Prior to the start of each cycle, decrease in blast percentage or stable disease (ie, not more than a 50% increase in blast percentage) based on the most recent bone marrow evaluation.
3. Recovery to grade 1 or baseline non-hematologic clinically significant test article-related toxicity (including liver function test abnormalities, not including alopecia).

4. Serum bilirubin $\leq 1.5 \times$ ULN, and AST or ALT $\leq 2.5 \times$ ULN (or if elevated due to tumor, bilirubin $\leq 2 \times$ ULN). Isolated AST or alkaline phosphatase elevations need not result in dose delays if not related to hepatobiliary organs (eg, alkaline phosphatase elevations due to bone involvement). Inotuzumab ozogamicin dosing should be permanently discontinued for any patients with possible, probable or confirmed VOD or other severe liver toxicity.
5. Any serum creatinine level associated with a measured or calculated creatinine clearance ≥ 15 mL/min using the method standard for the institution.
6. Prior to the start of each cycle, for subjects with pre-treatment ANC $\geq 1 \times 10^9/L$: ANC $\geq 1 \times 10^9/L$.
7. Prior to the start of each cycle, for subjects with pre-treatment platelets $\geq 50 \times 10^9/L$: platelets $\geq 50 \times 10^9/L$.
8. Subjects with pre-treatment ANC $< 1 \times 10^9/L$ and/or platelets $< 50 \times 10^9/L$: ANC and platelets must recover to baseline values obtained for the prior cycle, or ANC $\geq 1 \times 10^9/L$ and platelets $\geq 50 \times 10^9/L$, or the most recent bone marrow must demonstrate stable or improved disease, and the ANC and platelets are believed to be low due to disease.

There are no ANC or platelet count requirements for Cycle 1 day 1, as dosing criteria are relative to pre-treatment values. While doses given within a treatment cycle (ie, day 8) need not be delayed due to neutropenia or thrombocytopenia, dose delays within a cycle are recommended for non-hematologic toxicity.

Dose delays due to drug toxicity ≤ 7 days during a treatment cycle are permitted. Dose delays of > 7 days within a cycle will result in omission of the subsequent dose; the subject remains eligible to receive the subsequent planned doses. If a treatment interruption continues beyond day 14 of the current cycle, then the day when treatment is restarted will be considered day 1 of the next cycle. Dose delays due drug toxicity > 28 days at the end of a treatment cycle (ie, delay of day 1 dosing of subsequent cycle) will result in permanent discontinuation of study treatment. All toxicity grades are according to National Cancer Institute Common Terminology Criteria for Adverse Events version 4.03 (NCI CTCAE v 4.03).

8.1.6 Dose reductions

Dose reductions may also be required based on the worst toxicity experienced in the previous cycle. Patients experiencing a treatment interruption due drug toxicity ≥ 14 days may resume dosing at the next lower dose level (if a lower dose level is available) for the subsequent cycle once adequate recovery is achieved. Dose reductions to the next lower dose level (if a lower dose level is available) should also be considered for patients with CRI, whose platelet counts have not recovered to values obtained prior to the start of the previous cycle. Once a patient has a dose reduction for a drug-related toxicity, the dose will not be re-

escalated. Patient requiring more than two dose reductions will be withdrawn from treatment study.

Dose Level	Day 1 Dose (mg/m²)	Day 8 Dose (mg/m²)	Total dose Per Cycle (mg/m²)
0 (Starting dose beyond C1)	0.6	0.3	0.9
-1	0.4	0.2	0.6
-2	0.3	0.1	0.4

8.2 Drug storage and drug accountability

The amber vials of inotuzumab ozogamicin are to be stored at 2°C to 8°C (36°F to 46°F). Inotuzumab ozogamicin is light sensitive and should be protected from direct and indirect sunlight and unshielded fluorescent light during the preparation and administration of the infusion. Preparation of inotuzumab ozogamicin should occur in full compliance with institutional or local regulations for reconstitution of IV medications under aseptic conditions. Refer to the Dosage and Administration Instructions in the Study Manual for more information on stability, time frame of administration once reconstituted, and administration. Inotuzumab ozogamicin must be stored as indicated. Deviations from the storage requirements for any products supplied (shipped) by Pfizer, including any actions taken, must be documented and reported to Pfizer. Once a deviation is identified, the product must be quarantined and not used until Pfizer provides documentation of permission to use the investigational product. Inotuzumab ozogamicin will be labeled according to regulations. Storage conditions stated in the Investigator's Brochure may be superseded by the label storage.

The investigator must maintain a complete and current accountability record. Investigational product accountability applies to such products when they are required by the protocol and supplied (shipped) by the supporter. All unopened investigational product must be returned in the original containers to the supporter/contract distribution center with the appropriate form, or transferred to another site as applicable for this study. The site and the site monitor are to contact the supporter for detailed information before the transfer of investigational product to another site, or return to the supporter is to take place. Investigational product return must be documented on the accountability record. The site may destroy unused investigational product in an open container (ie, investigational product left after the vial was opened and/or reconstituted) and empty investigational product containers after accountability has been performed. Investigational product destruction must be documented on the accountability record. Investigational product is destroyed at the site only with the supporters permission. For this protocol, investigational product is destroyed at the site only

with the supporter's permission and after accountability has been performed by the supporter's monitor. The process of return, destruction, and accountability and reconciliation for controlled (eg, narcotics), hazardous (eg, investigational product used in oncology) and/or isotopically labeled substances, is performed in accordance with local laws and regulations. Shipment of an investigational product that is a hazardous substance or whose shipment may expose humans to risk will be done according to local laws and regulations.

8.3 Recommendations to reduce the risk of VOD for patients proceeding to ASCT

- For patients planning to receive an allogeneic ASCT, it is recommended that treatment with inotuzumab ozogamicin be limited to 2 cycles of induction or the fewest number of cycles required to achieve a CR/CRi/CRp (if CR/CRi/CRp not achieved after 2 cycles).
- The risk of relapse must be balanced against the potential risk of toxicity associated with beginning ASCT soon after the last dose of inotuzumab ozogamicin; however, approximately 5-6 weeks between inotuzumab and ASCT may be reasonable for most patients.
- Healthcare providers should use their clinical judgment to determine the most appropriate course of therapy for prophylactic treatment before the start of conditioning therapy according to standard of care (eg, prophylactic ursodeoxycholic acid at 12-15 mg/kg/day, beginning 2 weeks before the start of conditioning therapy).
- Use the least hepatotoxic conditioning regimen and, specifically, avoid using regimens that contain 2 alkylating agents and or that combine an alkylating agent with higher dose TBI (defined as >12 Gy).
- If using a busulfan-containing conditioning regimen, please consider using pharmacokinetically-dosed busulfan.
- When possible, avoid the concomitant use of hepatotoxic drugs peri-transplant.
- If significant liver toxicity occurs, consult a gastroenterology and/or hepatology service.
- When evaluating liver toxicity, inform the radiologist of the potential for hepatic vascular disease. When VOD is in the differential diagnosis, a right upper quadrant ultrasound with colorflow doppler (including resistive indices to hepatic artery flow and evaluation of hepatic venous outflow) should be performed. In addition, the radiology report should describe the degree of gall bladder wall thickening in millimeters and the volume of ascites should be estimated as closely as possible (i.e., small and localized, moderate and generalized, or large and generalized).
- Defibrotide may be used in the setting of severe VOD
- If a patient will proceed to ASCT under the care of different physicians, these recommendation should be reviewed with the new treating physicians.

9.0 Evaluation of Toxicity

Toxicities will be graded according to the NCI Common Terminology Criteria for Adverse Events (CTCAE) version 4.03.

10.0 Criteria for Removal from the Study

Criteria for removal from study include, but are not restricted to, the following:

10.1 No response after 2 cycles or progressive disease, unless considered by the treating physician and after discussion with the PI to be in the best interest of the patient. In this situation, if the treatment is well tolerated, patient can receive up to a maximum of 4 cycles.

10.2 Non-compliance by the patient with protocol requirements

10.3 Patient's request to be removed from the study

10.4 Occurrence of CTCAE grade 4 adverse event at least possibly related to inotuzumab. For CTCAE grade 4 adverse events that are numerically defined laboratory parameters, independent investigator assessment should be used to determine the risk:benefit for each individual patient to continue or discontinue inotuzumab treatment

10.5 Occurrence of an adverse event which makes discontinuation from treatment necessary due to protocol specified safety criteria or desirable in the investigator's and/or the subject's opinion

10.8 Investigator's decision that a subject does not benefit from treatment anymore, e.g., non-response or development of progressive disease

11.0 STATISTICAL CONSIDERATIONS

This is a single-arm phase II study of a single agent of low dose inotuzumab ozogamicin in adult patients with relapsed or refractory CD22-positive ALL. Patients will receive inotuzumab ozogamicin for up to 6 cycles. The primary endpoint of this study is hematologic remission, defined as CR + CRp + CRI occurred any time during the treatment. The Simon's optimal two-stage design will be used for interim futility monitoring. The null hypothesis is that the hematologic remission rate is 35% and our target rate under the alternative hypothesis is 50%. Under the design, we will enroll 18 patients in the first stage. If 6 or fewer patients achieve the primary endpoint, enrollment of future patients will be halted. If 7 or more out of the first 18 patients have met the primary endpoint, accrual will continue until a total of 48 patients are enrolled. If 21 or more out of these 48 patients achieve the primary endpoint, the treatment will be

considered efficacious and is worth further investigation. Under this Simon's optimal two-stage design, the type I error is 0.113, the power is 78.3%, the probability of early termination is 0.549 if the true hematologic remission rate is 35% and the expected sample size is 31.5 patients. After the first stage, if not at least 7 responders are observed in the first 18 patients, we will temporarily suspend the accrual until enough number of responders (i.e., $>/=7$) is reached.

We will also monitor treatment emergent toxicities using a Bayesian design by Thall, Simon and Estey [Thall PF, Simon RM, Estey EH. Bayesian sequential monitoring designs for single-arm clinical trials with multiple outcomes. *Statistics in medicine*. 1995;14(4):357-379], in cohort size of 8. For monitoring purpose, toxicities are defined as [any grade VOD that is deemed as related to inotuzumab] and the associated toxicity stopping rule is to stop the trial if $\text{Prob}\{p(\text{TOX}) > 0.20 | \text{data}\} > 0.92$, where $p(\text{TOX})$ is the toxicity rate and a beta(0.4, 1.6) distribution was assumed for the prior. That is, if at any time during the trial we determine that there is more than 92% chance that the toxicity rate is more than 20%, we will stop the trial due to safety concern. The corresponding stopping boundaries are shown in Table 3 below and the operating characteristics of the toxicity monitoring are illustrated in Table 4. Multc Lean Desktop (v2.1.0) (<https://biostatistics.mdanderson.org/SoftwareDownload/>) was used for generating the stopping boundaries and the OC table.

An Efficacy/Toxicity Summary will be submitted to the IND Office Medical Monitor, after the first 8 evaluable, and every 8 evaluable patients thereafter, in an accumulating method.

Table 3. Toxicity stopping boundaries in cohort size of 8.

Number of patients	Stop the trial if there are this many patients having toxicity
8	4-8
16	6-16
24	8-24
32	11-32
40	12-40
48	Always stop with this many patients

Table 4: Operating characteristics for toxicity monitoring.

True Toxicity Rate	Early Stopping Probability	Average number of patients treated	25 th , 75 th percentile
0.10	0.008	47.7	48, 48
0.15	0.05	46.4	48, 48
0.20	0.17	43.0	48, 48
0.25	0.40	37.1	24, 48
0.30	0.65	29.8	16, 48
0.35	0.85	23.0	8, 40
0.40	0.95	17.8	8, 24
0.45	0.99	14.3	8, 16

Analysis Plan:

The hematologic remission rate will be estimated along with the 95% credible interval. Data from all subjects who receive any study drug will be included in the safety analyses. Subjects who entered the study but did not take any of the study drug and had this confirmed will not be evaluated for safety. The severity of the toxicities will be graded according to the NCI CTCAE v4.03 whenever possible. We will follow standard reporting guidelines for adverse events. Safety data will be summarized by AE category, severity and frequency. The proportion of patients with AEs will be estimated, along with the Bayesian 95% credible interval. Kaplan-Meier method will be used to assess the overall survival (OS), progression-free survival (PFS), duration of response (DoR) and durations of remission (DoR1). The rate of hematologic response (CR + CRI + PR) will also be estimated.

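### Section 11.0 states 78.3% power, but the exact power of the stated two-stage rule is 78.5%; the other three design figures reproduce and no decision changes

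*Combined protocol and SAP*

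**What the plan says.** The design is set out in the first paragraph of section 11.0 (Statistical Considerations) of the combined protocol and SAP.

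- Design: "The Simon's optimal two-stage design will be used for interim futility monitoring".
- Rates, in per cent: "The null hypothesis is that the hematologic remission rate is 35% and our target rate under the alternative hypothesis is 50".
- First stage: "we will enroll 18 patients in the first stage", with the futility rule "If 6 or fewer patients achieve the primary endpoint, enrollment of future patients will be halted".
- Second stage: with 7 or more remissions, "accrual will continue until a total of 48 patients are enrolled".
- Final criterion: "If 21 or more out of these 48 patients achieve the primary endpoint, the treatment will be" judged efficacious and worth further study.
- Operating characteristics: "the type I error is 0.113, the power is 78.3%, the probability of early termination is 0.549" at a true rate of 35%, and "the expected sample size is 31.5 patients".

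All four operating characteristics are attributed to this one rule. The section names software for the toxicity boundaries and their operating characteristics, but names no software or method for the Simon figures.

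**The concern.** A Simon rule with fixed boundaries has exactly one power at a given response rate, and it is a finite binomial sum. The plan prints its four operating characteristics to three significant digits. Three agree with the rule to the last digit, and the power does not. Rounding cannot explain this, because 0.7853 does not round to 78.3%.

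What is at stake is small. The power is likely to be repeated when the trial is reported, and anyone who recomputes it from the stated boundaries will find that it differs. Nothing in the conduct of the trial depends on the third digit.

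**Working it through.** **Inputs, all from section 11.0.** Null rate 0.35; alternative rate 0.50; first stage n1 = 18, stop at r1 = 6 or fewer; total n = 48, so 30 patients in the second stage; success at 21 or more, so r = 20.

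**Formulas.** Let X1 be the number of remissions among the first 18 patients and X2 the number among the next 30, independent binomials with rate p.

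- Early termination: PET(p) = P(X1 ≤ 6).
- Probability of success: S(p) = sum over x = 7 to 18 of P(X1 = x) × P(X2 ≥ 21 − x). This is the type I error at p = 0.35 and the power at p = 0.50.
- Expected size: EN = 18 + (1 − PET) × 30.

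**The plan's figures at 35%.**

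- PET = P(Bin(18, 0.35) ≤ 6) = 0.5491. Stated 0.549: agrees.
- EN = 18 + (1 − 0.5491) × 30 = 18 + 13.53 = 31.53. Stated 31.5: agrees.
- S(0.35) = 0.1127. Stated 0.113: agrees.

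**Power at 50%, term by term.**

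| x of 18 | P(X1 = x) | Needed of 30 | P(X2 ≥ needed) | Product |
|---|---|---|---|---|
| 7 | 0.12140 | 14 | 0.70767 | 0.08591 |
| 8 | 0.16692 | 13 | 0.81920 | 0.13674 |
| 9 | 0.18547 | 12 | 0.89976 | 0.16688 |
| 10 | 0.16692 | 11 | 0.95063 | 0.15868 |
| 11 | 0.12140 | 10 | 0.97861 | 0.11880 |
| 12 | 0.07082 | 9 | 0.99194 | 0.07025 |
| 13 | 0.03268 | 8 | 0.99739 | 0.03260 |
| 14 | 0.01167 | 7 | 0.99928 | 0.01166 |
| 15 to 18 | 0.00377 | 6 or fewer | above 0.999 | 0.00377 |

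The sum is 0.78529, or 78.5%. A simulation of 4 million trials also gave 0.7853. The gap from the stated figure is 78.53 − 78.3 = 0.23 percentage points.

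**Which item is wrong: the power or a boundary?** Changing one element of the rule at a time gives the following.

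| Change | Figure at 35% that no longer matches | Power at 50% |
|---|---|---|
| Stop at ≤5 of 18 | PET 0.355 | 82.6% |
| Stop at ≤7 of 18 | PET 0.728 | 69.9% |
| Total 47 | EN 31.08 | 75.9% |
| Total 49 | EN 31.98 | 80.7% |
| Success at ≥20 of 48 | Type I error 0.166 | 82.8% |
| Success at ≥22 of 48 | Type I error 0.071 | 72.2% |

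With the stated 18 first-stage patients, PET fixes the first boundary, EN fixes the total and the type I error fixes the final boundary. Each points to the rule as written, and none of these alternatives has a power of 78.3%. A search for the Simon optimal design with type I error at most 0.113 and power at least 78.3% also returns 6/18 and 20/48. The power is therefore the one figure out of line.

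**The case against.** The strongest reply is that this has no consequence. The difference is 0.23 points, the stated value understates the power, and no one would plan or interpret the trial differently at 78.5%. That stands, and it sets the weight of the point.

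A second reply is that agreement this close should count as reproduction, since the figure could be a simulated value, a minimum-power limit from a design search, or a typing slip. Simulation is numerically plausible: with 10,000 runs (an assumption) the standard error is √(0.7853 × 0.2147 / 10,000) = 0.0041, or 0.41 points, larger than the gap. However, the documents describe no simulation for the Simon figures, and a loose tolerance does not suit an exact sum printed to 0.1 point. Under any of these explanations the printed number is still not the power of the stated rule.

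A reader might go further and infer that the power was calculated for a different design, so that the boundaries are in doubt. The documents do not support that. For example, the same first stage followed by success at 17 or more of 39 has power 0.7828, which looks like a match. But its type I error is 0.147 and its expected size is 18 + (1 − 0.5491) × 21 = 27.5, against the stated 0.113 and 31.5. The figures that do agree belong to 6/18 and 20/48.

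**Conclusion.** The stated power is wrong as written: 78.3% should read 78.5% (exact value 0.7853). It is a minor numerical correction in the conservative direction. Both boundaries, the sample size of 48, the type I error, the early-termination probability and the expected size all stand, and no decision changes. The mismatch does not show that the design was miscalculated, and the boundaries need no re-confirmation on account of it.

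The result assumes independent patients with a common remission rate, and the futility and success rules exactly as stated. It concerns the Simon rule taken alone. The VOD stopping rule is described afterwards as separate monitoring and is not part of this calculation. The sentence on suspending accrual until 7 responders are reached is read as a pause while response data mature, so it does not enter the sum either.

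**What to change.** In section 11.0, replace the power of 78.3% with 78.5%, and leave the rest of the paragraph's design figures as they are. The cost is one number at the next amendment. It needs no redesign and has no statistical or operational downside.

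### The stated power and Table 4's average number treated are each worked out under one stopping rule alone, although both rules stop the same 48-patient trial

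*Combined protocol and SAP*

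**What the plan says.** All of this is in section 11.0, Statistical Considerations.

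- **Efficacy rule.** Null remission rate 35%, target 50%. After 18 patients, "If 6 or fewer patients achieve the primary endpoint, enrollment of future patients will be halted". Otherwise "accrual will continue until a total of 48 patients are enrolled". The treatment counts as efficacious on this condition: "If 21 or more out of these 48 patients achieve the primary endpoint".
- **Figures for that rule.** "the type I error is 0.113, the power is 78.3%, the probability of early termination is 0.549" at 35% remission, with an expected sample size of 31.5. They are introduced as properties of the Simon design. VOD stopping is not mentioned.
- **VOD rule.** The trial stops if the posterior probability that the rate of inotuzumab-related VOD exceeds 20% is above 0.92, with a beta(0.4, 1.6) prior. Table 3 turns this into stopping at 4 of 8, 6 of 16, 8 of 24, 11 of 32 or 12 of 40.
- **Figures for that rule.** The plan says that "the operating characteristics of the toxicity monitoring are illustrated in Table 4". Table 4 gives stopping probability, average number treated and quartiles by true toxicity rate. The futility look is not mentioned.

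No joint figures are given, and neither block says that it leaves out the other rule.

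**The concern.** A trial stopped for VOD cannot reach 21 remissions in 48 patients, so the chance of a positive result depends on the VOD rate as well as the remission rate. Likewise, a trial stopped for futility at 18 does not go on to treat 48, so the average number treated depends on the remission rate as well as the VOD rate.

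The two blocks can be compared on the page. The Simon paragraph expects 31.5 patients at 35% remission, while Table 4 averages 47.7 at 10% VOD. Adding a second stopping rule can only lower an average, so 47.7 cannot describe this trial if remission is at the null rate.

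This matters because section 7.1 states the aim as less VOD without loss of efficacy. Readers therefore need the behaviour of the two rules together, and the plan gives each only in isolation.

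**Working it through.** **Inputs.** Futility rule, success rule and Table 3 boundaries are from section 11.0. VOD scenarios: 10% (section 7.1), 14% any grade (section 7.4) and 20% (the threshold in section 11.0), with 5% and 25% for range. Remission scenarios: 35% and 50% (section 11.0) and 80% (section 7.1). The documents give no dependence between remission and VOD. Independence is assumed first and then varied. Each look is taken to have complete outcomes for the patients counted.

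**Step 1: Simon rule alone.** With X1 ~ Bin(18, p) and X2 ~ Bin(30, p):
- F = Pr(early termination) = Pr(X1 ≤ 6)
- Pr(success) = Σ over x = 7 to 18 of Pr(X1 = x) · Pr(X2 ≥ 21 − x)
- Expected N = 18 + 30(1 − F)

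At p = 0.35: F = 0.5491, type I error 0.1127, expected N = 18 + 30 × 0.4509 = 31.53. These reproduce 0.549, 0.113 and 31.5. At p = 0.50: F = 0.1189 and power 0.7853, that is 78.5% against 78.3% printed. At p = 0.80: F is about 0.00002.

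**Step 2: VOD rule alone.** Let s_n be the probability that the Table 3 boundary is first met at look n, found by carrying the binomial counts forward in blocks of 8. Let S be the sum of the s_n. Average N = Σ n·s_n + 48(1 − S). At VOD 10, 15, 20, 25 and 30%:
- S = 0.008, 0.050, 0.174, 0.397, 0.652
- average N = 47.7, 46.4, 43.0, 37.1, 29.8

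These match Table 4, as do the rows at 35 to 45%, so Table 4 contains no futility stop. The boundaries also follow from the posterior rule. The closest case, 10 of 32, gives 0.9195, just below 0.92, so 11 is right.

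**Step 3: both rules, independent outcomes.** The futility look at 18 falls between the VOD looks at 16 and 24.
- Pr(success) = Pr(success, Simon alone) × (1 − S)
- Average N = 8·s8 + 16·s16 + 18·F·(1 − s8 − s16) + (1 − F)·[24·s24 + 32·s32 + 40·s40 + 48(1 − S)]

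At 10% VOD: s8 = 0.00502, s16 = 0.00218, s24 = 0.00076, s32 = 0.00003, s40 = 0.00015, S = 0.0082.
- 50% remission: 0.040 + 0.035 + 2.126 + 0.022 + 41.946 = 44.2
- 35% remission: 0.040 + 0.035 + 9.813 + 0.011 + 21.467 = 31.4

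In each sum the fourth term combines the looks at 24, 32 and 40.

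Power at 50% remission: 0.7853 × (1 − 0.0082) = 0.779 at 10% VOD; 0.7853 × (1 − 0.0366) = 0.757 at 14%; 0.7853 × (1 − 0.1742) = 0.649 at 20%.

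| VOD | Average N, VOD rule alone | Both rules, 35% remission | Both, 50% | Both, 80% | Power at 50% | Type I error at 35% |
|---|---|---|---|---|---|---|
| 5% | 48.0 | 31.5 | 44.4 | 48.0 | 78.5% | 0.113 |
| 10% | 47.7 | 31.4 | 44.2 | 47.7 | 77.9% | 0.112 |
| 14% | 46.8 | 30.9 | 43.4 | 46.8 | 75.7% | 0.109 |
| 20% | 43.0 | 28.9 | 40.0 | 43.0 | 64.9% | 0.093 |
| 25% | 37.1 | 25.9 | 34.7 | 37.1 | 47.3% | 0.068 |

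**Step 4: dependence.** Two extremes were simulated, 400,000 trials each: VOD only in responders, and VOD only in non-responders. Power at 50% remission ranges over 77.7 to 78.2% at 10% VOD, 75.0 to 76.8% at 14%, and 62.0 to 68.8% at 20%. Average N at 10% VOD stays at 31.3 to 31.5 (35% remission) and 44.1 to 44.2 (50%).

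**The case against.** The strongest reply is that each block is labelled by its own rule and, apart from 0.2 points of power, is right under that rule. Reporting separate rules separately is common practice. That stands: a reader might infer that section 11.0 is arithmetically wrong throughout, and the reproduction in steps 1 and 2 shows that it is not. The label does not fully help Table 4, however, because an average number treated reads as a property of the trial.

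Further points, and what remains of each:

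- **The null expected size is sound.** With both rules it is 31.4 at 10% VOD against 31.5 printed. This stands.
- **Power hardly moves at 10% VOD, and the study aims lower.** This stands. The 14% rate comes from the comparative trial in section 7.4, where 10 of the 15 cases followed later transplant, so it is a scenario and not a forecast.
- **The large losses of power occur at 20% VOD and above.** A reader might infer from 64.9% or 47.3% that the trial is underpowered. The documents do not support that, because halting a drug with too much VOD is what the rule is for.
- **Early stopping.** A reader might set the chance of any early stop at 10% VOD (0.553 at 35% remission, 0.126 at 50%) against Table 4's 0.008. These are different quantities: 0.008 is stopping for toxicity only, and the plan already discloses 0.549 for futility at the null.
- **The gap in average N disappears at high remission.** At the 80% response reported in section 7.1, Table 4 stands. The gap applies at the 35% and 50% rates on which the trial was sized.

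**Conclusion.** This is a gap in the reported operating characteristics. The design itself does not fail: the boundaries are correct, and leaving out the VOD rule overstates type I error, so no false-positive risk is hidden.

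The main effect is on Table 4's average number treated. At 10% VOD it is too high by 47.7 − 31.4 = 16.3 patients at the null remission rate and by 47.7 − 44.2 = 3.5 at the target. At 20% VOD the excess is 43.0 − 28.9 = 14.1 and 43.0 − 40.0 = 3.0. At 80% remission there is no excess.

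The effect on power is small at 10% VOD (77.9%), modest at 14% (75.7%) and large only at the 20% safety threshold (64.9%, or 62 to 69% across the dependence extremes). Separately, the Simon-only power should read 78.5%.

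The point values assume that remission and VOD are independent and that outcomes are complete at each look. A reader might go further and infer that the sample size or the approval rested on materially wrong figures. The documents do not show that: no boundary, sample size or decision rule changes.

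**What to change.** 1. Correct the Simon-only power to 78.5%, and state that the Simon figures exclude stopping for VOD.
2. Replace Table 4's average-number-treated column with joint values, or add them beside it, for remission of 35, 50 and 80% and VOD from 5 to 25%.
3. For each combination, give separate probabilities of success, of a futility stop and of a VOD stop. At 50% remission and 10% VOD, for example, these are 0.779, 0.118 and 0.008. The remaining 0.095 (1 − 0.779 − 0.118 − 0.008) is completion with fewer than 21 remissions.
4. State the independence assumption, with the range under dependence as a sensitivity check.

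Boundaries and sample size do not change. The cost is one recomputed table and a slightly less favourable power once VOD stopping is counted. If the sponsor prefers to leave the table alone, the minimum is a sentence saying that each set of figures ignores the other rule, though the reader would then still lack the trial's actual average size.
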